**7.1.2. Exclusion criteria**

**Table 4: Exclusion criteria**

Organic vocal pathology 1) Structural/neoplastic disorders (e.g. carcinoma, cyst, polyp, papilloma, Reinke’s oedema); 2) neurological disorders (e.g. vocal cord palsy, paresis, spasmodic dysphonia); 3) inflammation (e.g. infection, reflux (RFS >7) or significant relevant systemic disease (e.g. severe COPD) or need for surgery

---------------------------------------------------------------------------------------------------------------------------------------------------------------------------------------------------------------------------------------------------------------------------------------------------------------------------------------------------

SHORT TITLE/ACRONYM: CVT4MTD

IRAS:306954

Significant psychological issues identified during initial assessment (with option to withdraw if discovered during the treatment periods and agreed by both patient and Therapist)

MDT pattern (IV-VI) compatible with significant primary psychological aetiology on laryngoscopy

Transgender voice issues

Previously incompletely treated dysphonia, neurological disease, or upper aerodigestive tract malignancy

Had previous VT or CVT training or pharmacological treatment for their voice problem (other than proton pump inhibitors or an alginate recommended for disorders of laryngopharyngeal reflux-related symptoms)

A hearing impairment that would prohibit or impact on telepractice treatment

Significant concomitant health problems affecting voice

Not have or be able to use a computer with video link at home or in hospital even with support

Not able to commit to the study protocol

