### Treating CVT Practitioner (t=0 to t=6)

Up to 6 sessions (45-60 mins) given online over a total of 6/52

- Medical/SLT assessment documentation available to Practitioner
- Assessment by treating Practitioner and treatment plan including goals agreed with patient
- Structured proforma documenting session goals, and % time of therapy used in each session completed at end of each session to form part of treatment record
- Observation by study SLT-VT, and/or recording of sessions
- Review of progress (log of treatment and study SLT -V observations where performed) by study SLT-V, study CVT-P and Laryngologist after 2 and 4 therapy sessions

If concerns about suitability of treatment for patient, they may exit the study after agreement between study team and patient

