## 5. STUDY DESIGN AND METHODS OF DATA COLLECTION AND STATISTICAL ANALYSIS PLAN

The aim of this proof-of-concept study is to evaluate whether the approach used in the Complete Vocal Technique to improve voice production in singers and performers can be applied to patients with Type I-III Muscle Tension Dysphonia pattern using a Telehealth medium. Ten consecutive patients seen in an NHS Joint SLT/ENT Voice clinic who meet the inclusion/exclusion criteria and who give consent will be invited to take part in the study. In addition, MTD patients awaiting SLT-VT will be invited to take part in the study. Data including validated patient self-assessment questionnaires, audio-perceptual evaluation of the voice, acoustic and EGG recordings of the voice and an aerodynamic measure (MPT), will be collected after recruitment in a research clinic at the beginning of the study (t=0) and again at the end of the study (t=8). Data will be collected by the study Laryngologist or study SLT. Additional questionnaires will also be given to patients and Therapists at the end of the study to obtain feedback on satisfaction with achievement of goals, the therapy, and the use of Teletherapy to deliver the treatment. Quantitative standard descriptive and inferential statistics methods will be applied to compare pre-and post-therapy measures using the VHI as the primary outcome measure as well as the selected secondary outcome measures.

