### VHI

Paired-samples t tests will be applied to the pre-treatment and post-treatment primary outcome measure scores (total VHI score).

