### Acoustic, EGG and MPT measures

Paired-samples t tests will also be applied to the secondary acoustic outcome measures (EGG, acoustic and MPT measures), together with 95% confidence intervals.

To control for Type 1 error of the primary outcome and secondary outcome analyses while maintaining an acceptable level of statistical power, the alpha level for all t-test comparisons will also be assessed at .025. Treatment effects will be assessed by comparing the pre-treatment to post-treatment change ( $\Delta$ ) scores, plotted as a forest plot in order to display the average  $\Delta$  change for each outcome measure and corresponding 95% confidence interval. Any significant treatment effects will be followed up with calculations of effect size using Cohen's d.

SHORT TITLE/ACRONYM: CVT4MTD

IRAS:306954

Measurement reliability for acoustic analyses will be calculated by reanalysis of 10% of the recordings. The recordings chosen for reliability analysis will be randomly selected from the total number of recordings. Pearson product–moment correlations will be used to assess inter-measurer and intra-measurer reliability of the acoustic and EGG measurements.

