### 7.2.1. Size of sample

As this is a proof-of-concept study the sample size of ten patients was selected arbitrarily to generate the necessary results for a power analysis for future studies.

SHORT TITLE/ACRONYM: CVT4MTD

IRAS:306954

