## 8. ETHICAL AND REGULATORY CONSIDERATIONS

### 8.1. Assessment and management of risk

The main risk is of failure to improve with treatment although this is thought to be minimal as this pilot study involves administration of existing types of therapy applied to singers. The study treatment session documentation will be reviewed by the study Laryngologist, Speech and CVT therapists after the second and fourth treatment sessions. Ad hoc observation of the CVT-P treatment sessions will be made by the Study SLT-VT if the patient has given consent. The patient, recordings and questionnaires will be reviewed at the research clinic appointment at the end of the study (t=8) and

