**CONFIDENTIAL**

Page **25** of **39**

SHORT TITLE/ACRONYM: CVT4MTD

IRAS:306954

contracts and be subject to Trust employment terms and conditions, undergo GCP training, the therapy would be overseen by the study SLT-V who would observe some of the sessions and a review progress after second session. All patients could withdraw from the study at any time and the patients would all be reviewed at eight weeks to determine if their goals of therapy had been met and whether further assessment of treatment was required.

In addition, the protocol with a questionnaire (see [19ET004 Appendix G CVT4MDT Patient & Public Involvement & Engagement survey sheet v0.3 V1.0 12 Jan 2022](#)) was given to five patients attending the Joint Voice clinic on 14th December 2021. Two patients had MTD and the rest had other voice problems. The results were overall very positive.

SHORT TITLE/ACRONYM: CVT4MTD

IRAS:306954

1) Did you understand the information given in the sheet?

Yes = 5 No = 0

Is there anything which isn't clear? No comments

2) Having read through the info sheet, would you theoretically consider taking part in this study?

Yes = 5 No = 0

Please say why or why not? No comments

3) Do you think the aim of this pilot study, to test whether CVT-VT used in performers can help patients with MTD, is a good idea?

Yes = 5 No = 0

If No, please say why not?

It seems useful & practical

The project sounds very helpful.

If CVT-VT therapy works this can support recovery more quickly

4) Do you have any concerns about patients having therapy with a specialist vocal coach (CVT-VT) rather than a Speech & Language therapist (SLT-VT) in this study?

Yes = 1 No = 4

If Yes, please say why? No comments

Are CVT as good as SLT? Are they medical people?

Giving patients every chance to heal their voice early rather than waiting at length for an ENT appointment

5) Do you have any concerns or comments about receiving your therapy using a video link?

Yes = 0 No = 5

If Yes, please say why? No comments

6) If you were a participant, would you be happy, have no strong opinion or be unhappy if the therapy sessions were recorded for more detailed analysis (please circle)?

Happy = 4 No strong opinion = 1 Unhappy = 0

7) If you were a participant, would you be happy, have no strong opinion or be unhappy if a specialist Speech and Language Voice Therapist observed the CVT Therapy sessions (please circle)?

Happy = 5 No strong opinion = 0 Unhappy = 0

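### A patient who stops therapy can be lost from the paired VHI analysis: state that the t=8 VHI is still requested and used

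*Combined protocol and SAP*

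**What the plan says.** Two places let a patient leave during treatment.

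- Flow chart text, Treating CVT Practitioner (t=0 to t=6), directly after the progress reviews that follow sessions 2 and 4: "If concerns about suitability of treatment for patient, they may exit the study after agreement between study team and patient".
- Section 7.1.2, Table 4, attached to the exclusion for significant psychological issues: "with option to withdraw if discovered during the treatment periods and agreed by both patient and Therapist". The table does not say what the patient withdraws from.

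The primary analysis is in section 5 under VHI: "Paired-samples t tests will be applied to the pre-treatment and post-treatment primary outcome measure scores (total VHI score"). Sections 5 and 7.2 and Appendix H place the outcome questionnaires at the t=0 and t=8 research clinics and nowhere between.

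Four statements bear on what happens afterwards.

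- Section 8.3, Patient & Public Involvement: "All patients could withdraw from the study at any time and the patients would all be reviewed at eight weeks". The stated purpose is to see whether goals were met and whether more care is needed.
- Section 8.1 describes a review of the patient and the questionnaires at t=8.
- The flow chart text for the final session lists repeat questionnaires and sets no completion condition.
- Section 4.2 defines the main outcome after at most six sessions, so completing all six is not required.

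**The concern.** A decision about treatment (this therapy does not suit this patient) is written as a decision about the study (this patient leaves). A site that follows the flow chart text literally could release the patient from the t=8 visit. There is no intermediate outcome VHI to fall back on, and a paired t test uses only patients with both scores. The primary result would then describe those who stayed in the study, although the section 4.2 outcome also fits patients who stop early.

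The study has ten patients and no control group, so each pair is a tenth of the primary data. The results are also meant to feed the power calculation for later work (section 7.2.1), and the reasons for stopping are themselves feasibility information.

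**Working it through.** **Step 1: do the documents settle it?**

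| Place | Says about leaving | Says about VHI afterwards |
|---|---|---|
| Flow chart text, treating practitioner | Exit is from the study | Nothing |
| Table 4 | Withdrawal, object not named | Nothing |
| Section 8.3 | Withdrawal from the study at any time | Review of all at eight weeks; VHI not named |
| Section 8.1 | Nothing | Questionnaires reviewed at t=8; withdrawn patients not mentioned |
| Flow chart text, final session | Nothing | Questionnaires repeated; withdrawn patients not mentioned |
| Section 4.2 | Nothing | Outcome not conditional on completing therapy |

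No section says that VHI is requested or analysed after exit. No analysis set or missing-data rule is stated. The last four rows lean towards collection, and the first leans against it.

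**Step 2: inputs for size.** The sample is ten, and section 7.2.1 says that "the sample size of ten patients was selected arbitrarily to generate the necessary results for a power analysis for future studies". The plan gives no power, SD or dropout figure, so there is no stated calculation to reproduce. Three quantities are assumed for illustration: k patients of ten have no t=8 VHI; their change is a fraction r of the completers' mean change; and the completers' mean change is 1.0 SD of the paired changes.

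**Step 3: shift in the mean.** If completers change by m on average, the all-ten mean is m[(10 − k) + kr]/10. The ratio of completer mean to all-ten mean is 10/[(10 − k) + kr]. With m = 1.0 SD, the shift is 1 − [(10 − k) + kr]/10 SD.

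| r | k=1: ratio | k=1: shift (SD) | k=2: ratio | k=2: shift (SD) |
|---|---|---|---|---|
| 0 | 10/9 = 1.11 | +0.10 | 10/8 = 1.25 | +0.20 |
| 0.5 | 10/9.5 = 1.05 | +0.05 | 10/9 = 1.11 | +0.10 |
| 1 | 1.00 | 0 | 1.00 | 0 |
| 1.5 | 10/10.5 = 0.95 | −0.05 | 10/11 = 0.91 | −0.10 |

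**Step 4: precision.** The half-width of the 95% interval, in SD of the change, is t(0.975, n − 1)/√n.

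- n = 10: 0.715
- n = 9: 0.769, and 0.769/0.715 = 1.07
- n = 8: 0.836, and 0.836/0.715 = 1.17

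The largest shifts in Step 3 (0.10 SD with nine pairs, 0.20 SD with eight) are 0.10/0.769 = 13% and 0.20/0.836 = 24% of the matching half-width.

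**Step 5: does the interval always widen?** Only if the SD is held fixed. Suppose nine completers have SD s and the lost patient lies d·s from their mean. The all-ten variance is then s²(8 + 0.9d²)/9. The all-ten half-width, 0.715·√[(8 + 0.9d²)/9], equals 0.769 at d ≈ 1.63. At d = 2 it is 0.81, wider than the completers' 0.77. In the one-patient illustration above, d = |1 − r| is at most 1, so the interval does widen there.

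**The case against.** The best reply is that the sponsor already intends to see everyone at t=8. Section 8.3 puts withdrawal and an eight-week review of all patients in one sentence, the final-session text has no completion condition, and section 4.2 does not require six sessions. This stands as evidence of intent. It does not close the gap: section 8.3 summarises a public involvement discussion and describes a care review, and the operational text still has the patient leaving the study. If the intent is as suggested, the change only writes it where staff will look.

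A second reply is that any missing t=8 score has the same effect, whatever its cause. That is true, and the change cannot recover patients who decline the visit.

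Four stronger readings are tempting and are not supported.

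- *Patients who stop are dropped by rule.* No section says so.
- *Poor responders are removed and the result is inflated.* The flow chart exit follows the progress reviews, so this is conceivable. But its stated ground is suitability, Table 4's is a psychological issue, and neither is defined by response. The direction is unknown.
- *The two routes conflict over who decides.* Section 8.1 counts the CVT practitioners as study team members and the triggers differ, so the wordings are not contradictory.
- *Table 4 must be confined to t=0 and such patients kept in the primary analysis.* Whether a patient with a later-found exclusion belongs in the primary estimate is a choice of target population. Either answer is defensible.

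**Conclusion.** The point holds as a correction to wording with a direct link to the primary analysis. As written, the flow chart text allows a treatment-suitability concern to end study participation. Table 4 leaves the same possibility open, and nothing elsewhere secures the t=8 VHI afterwards. A patient who goes by either route can therefore be lost from the paired test.

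The size is modest. One or two lost pairs widen the 95% interval by 7% or 17% if the SD is unchanged. For r between 0 and 1.5 and a completer mean of 1.0 SD, the mean shifts by between −0.10 and +0.20 SD, against a half-width of 0.72 SD with all ten. The values of k, r and the mean change are assumptions; the documents supply none of them. This is a low-cost improvement to consider, not a threat to the study.

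The participant information sheet and consent form (Appendices E and F) were not available and the flow diagram image is not shown, so any withdrawal terms there could not be checked.

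**What to change.** - In the flow chart text and in Table 4, say that stopping CVT-VT is discontinuation of treatment and not exit from the study, and that the reason and the number of sessions received are recorded.
- In section 5, add a sentence: unless the patient declines, VHI is requested at the planned t=8 visit after therapy has stopped, and it is used in the paired VHI analysis, consistent with the section 4.2 definition.
- For patients stopped because of a psychological issue found after entry, report the result with and without them. The sponsor chooses in advance which is primary.

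The patient's own right to withdraw is untouched, and the clinical grounds for stopping stay with the sponsor.

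The cost is wording in two places and one or two sentences in section 5, with no new visit. There are two downsides: someone who has stopped therapy is asked to attend at t=8, and the mean change may come out slightly less favourable.

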## 7.2. Sampling

The paper questionnaires and forms will be completed by patients during the attendance at the research clinic at (t=0) and (t=8) and administered by the study Laryngologist and SLT-VT and form part of the Case Report Form (CRF). The acoustic and EGG voice recordings will also be made at these research clinic appointments by a member of the study team. CRFs and study documentation will be stored in a locked cabinet in a locked ENT department room. Questionnaire and other form data will be transcribed onto a digital platform and kept in patient folders in a secure Network storage area and a copy of relevant clinical data will also form part of the patient's digital health record (DHR). Acoustic and EGG data will be similarly stored with print outs of summary statistics forming part of the patient's DHR and CRF.

### 7.2.1. Size of sample

As this is a proof-of-concept study the sample size of ten patients was selected arbitrarily to generate the necessary results for a power analysis for future studies.

SHORT TITLE/ACRONYM: CVT4MTD

IRAS:306954

### 7.2.2. Sampling technique

## 7.3. Recruitment

All patients presenting to Joint Voice Clinic in the ENT Department at the Queen's Medical Centre, Nottingham University Hospitals with a diagnosis of MTD will be considered. In addition, patients with a diagnosis of MTD who are on the waiting list for SLT-VT will be invited to take part in the study. Those who meet the inclusion and exclusion criteria will be invited to take part in the study ([Appendix D\\_CVT4MTD\\_Invitation to Patient on WL for treatment of MTD- v0.01 2021\\_12\\_29](#)). The aim is to maximise the number of patients in a relatively short time frame.

### 7.3.1. Sample identification

The study will be publicized to all ENT and SLT staff within the department. Patients will then be highlighted to the study Laryngologist and SLT who will then arrange for them to be initially reviewed in the Joint Voice clinic. Travel and parking fees for the two additional trips to the hospital that will be involved in this study or if the patient has to attend because it is not possible to establish a video link with them at home.

### 7.3.2. Consent

Informed consent will be obtained prior to the participant undergoing any activities that are specifically for the purposes of the study. Identification of patients with capacity, who meet the inclusion and exclusion criteria will be given a patient information leaflet ([See 19ET004 Appendix E CVT4MDT Participant information sheet V2.0 21 Mar 2022](#)) outlining the protocol will be provided in the voice clinic. Those patients will then be contacted by phone and those who are willing to take part will be invited to the research clinic. They will have an opportunity to ask further questions and those that agree will be formally consented ([see 19ET004 Appendix F CVT4MTD\\_Informed-Consent-Form V2.0 21 Mar 2022](#))

## 8. ETHICAL AND REGULATORY CONSIDERATIONS

### 8.1. Assessment and management of risk

The main risk is of failure to improve with treatment although this is thought to be minimal as this pilot study involves administration of existing types of therapy applied to singers. The study treatment session documentation will be reviewed by the study Laryngologist, Speech and CVT therapists after the second and fourth treatment sessions. Ad hoc observation of the CVT-P treatment sessions will be made by the Study SLT-VT if the patient has given consent. The patient, recordings and questionnaires will be reviewed at the research clinic appointment at the end of the study (t=8) and

**CONFIDENTIAL**Page **24** of **39**

SHORT TITLE/ACRONYM: CVT4MTD

IRAS:306954

patients offered further assessment and treatment as necessary. If the researcher or therapist were to come into information which had safeguarding implications or discloses information where the patient has the potential to be exposed to risk or harm or to cause harm to others, this would be raised in the first instance with the Chief Investigator who would escalate the issue according to NUH's safeguarding policy or clinical teams. All members of the study team, including the CVT-Ps, will have contracts or honorary contracts with NUH, have undergone pre-employment checks including safeguarding and GCP training.

## **8.2. Research Ethics Committee (REC) review & reports**

Before the start of the study, approval will be sought from the REC at NUH to approve the study protocol, informed consent forms and other relevant documents. Any substantial amendments that require review by REC will not be implemented until the REC grants a favourable opinion for the study.

### **For NHS REC reviewed research**

- If the study is ended prematurely, the Chief Investigator will notify the REC, including the reasons for the premature termination.
- Within one year after the end of the study, the Chief Investigator will submit a final report with the results, including any publications/abstracts, to the HRA.

## **8.3. Peer review**

Initial approval was obtained by the Innovation Fund Denmark when successfully obtaining funding for the the whole project and was discussed with The NUH SLT team. The CVT treatment protocols and assessment methods were discussed with other experienced CVT teachers at the Complete Vocal Institute in Copenhagen. The CVT-VT treatment protocols and assessment methods were also discussed within the wider Speech Therapy team in the ENT Department at NUH. External Peer review has been obtained from [name], Director of Oxford Institute of Nursing, Midwifery and Allied Health Research, Oxford Brookes and Oxford Universities and [name], Advanced Practitioner SLT at Nottingham University Hospital, Director of H F Robinson Ltd and SVS Training Ltd and previous Head of Service for Speech & Language Therapy Nottinghamshire Healthcare.

## **Patient & Public Involvement**

The project was discussed at a PPIE drop-in session on 2nd December 2021. The group consisted of experienced research reviewers. Feedback was that the project was interesting, and the aims were clear. There was a question about governance, safeguarding and supervision of the CVT-P. The panel were reassured that all non-clinical members of the study team and the CVT-P would have honorary Trust

**CONFIDENTIAL**

Page **25** of **39**

SHORT TITLE/ACRONYM: CVT4MTD

IRAS:306954

contracts and be subject to Trust employment terms and conditions, undergo GCP training, the therapy would be overseen by the study SLT-V who would observe some of the sessions and a review progress after second session. All patients could withdraw from the study at any time and the patients would all be reviewed at eight weeks to determine if their goals of therapy had been met and whether further assessment of treatment was required.

In addition, the protocol with a questionnaire (see [19ET004 Appendix G CVT4MDT Patient & Public Involvement & Engagement survey sheet v0.3 V1.0 12 Jan 2022](#)) was given to five patients attending the Joint Voice clinic on 14th December 2021. Two patients had MTD and the rest had other voice problems. The results were overall very positive.

SHORT TITLE/ACRONYM: CVT4MTD

IRAS:306954

1) Did you understand the information given in the sheet?

Yes = 5 No = 0

Is there anything which isn't clear? No comments

2) Having read through the info sheet, would you theoretically consider taking part in this study?

Yes = 5 No = 0

Please say why or why not? No comments

3) Do you think the aim of this pilot study, to test whether CVT-VT used in performers can help patients with MTD, is a good idea?

Yes = 5 No = 0

If No, please say why not?

It seems useful & practical

The project sounds very helpful.

If CVT-VT therapy works this can support recovery more quickly

4) Do you have any concerns about patients having therapy with a specialist vocal coach (CVT-VT) rather than a Speech & Language therapist (SLT-VT) in this study?

Yes = 1 No = 4

If Yes, please say why? No comments

Are CVT as good as SLT? Are they medical people?

Giving patients every chance to heal their voice early rather than waiting at length for an ENT appointment

5) Do you have any concerns or comments about receiving your therapy using a video link?

Yes = 0 No = 5

If Yes, please say why? No comments

6) If you were a participant, would you be happy, have no strong opinion or be unhappy if the therapy sessions were recorded for more detailed analysis (please circle)?

Happy = 4 No strong opinion = 1 Unhappy = 0

7) If you were a participant, would you be happy, have no strong opinion or be unhappy if a specialist Speech and Language Voice Therapist observed the CVT Therapy sessions (please circle)?

Happy = 5 No strong opinion = 0 Unhappy = 0

8) Do you have any other comments or suggestions about the project?

9) Finally, would you be happy to be contacted in the future to give feedback on this or other voice related studies?

